6.3. Other restrictions and contraindications

Antroquinonol is contraindicated in patients who are hypersensitive to components of this product. Since antroquinonol primarily inhibits CYP3A4, some foods that are known to inhibit, induce, or serve as a substrate of CYP3A4 are potential contraindications to administration and should be avoided. These foods include charbroiled food, star fruit, and grapefruit juice. In addition, cruciferous vegetables should not be consumed within an appropriate time interval of study treatment dosing (at least 30 minutes). Alcohol or drug abuse is prohibited during the study. Social drinking is allowed; however, excessive alcohol use or binge drinking is discouraged during the study. In addition, smoking or vaping use is discouraged at least to Day 14, which is the primary endpoint.

7. STUDY ASSESSMENTS AND PROCEDURES

Study procedures and their timing are summarized in the Schedule of Assessments ([Appendix 5](#)). As protocol waivers or exemptions are not allowed, with the exception of immediate safety concerns, deviations should be discussed with the sponsor immediately upon occurrence or awareness to determine if the patient should continue or discontinue the study treatment. Adherence to the study design requirements, including those specified in the Schedule of Assessments, is essential and required for study conduct.

All screening evaluations must be completed and reviewed to confirm that potential patients meet all eligibility criteria. The investigator will maintain a screening log to record details of all patients screened and to confirm eligibility or record reasons for screening failure ([Section 4.4.1](#)), as applicable. Procedures conducted as part of the patient's routine clinical management (eg, blood count) and obtained before signing the informed consent form (ICF) may be utilized for screening or baseline purposes provided the procedure met the protocol-specified criteria and was performed within the timeframe defined in the Schedule of Assessments ([Appendix 5](#)). Additionally, patients will receive instructions for home administration of study treatment and a diary to capture all doses after a discharge.

Results of the confirmatory COVID-19 test already done as SoC can be used to determine eligibility. The test does not need to be repeated at screening if already confirmed and documented. A confirmatory test may be done at screening if the COVID-19 test is not documented as SoC.

At screening, laboratory tests and ECGs will be performed locally, as applicable, to assess eligibility and do not need to be repeated if already done as SoC (eg, within 24 to 48 hours of screening and patient is clinically stable). Chest x-ray or CT scan will be performed, as applicable, to assess eligibility and does not need to be repeated if done within 48 hours of screening. In addition, baseline central laboratory test samples can be taken after confirming eligibility. Baseline laboratory samples can be obtained at screening or on Day 1 (predose). Postbaseline laboratory samples do not need to be taken predose.

7.1. Efficacy Assessments

Efficacy assessment will be based on the clinical status of the patient during the study.

7.1.1. Primary efficacy endpoint

The primary efficacy endpoint is related to the proportion of patients alive and free of respiratory failure (ie, no need for invasive mechanical ventilation, non-invasive ventilation, high-flow oxygen, or ECMO) on Day 14.

7.1.2. Secondary efficacy endpoints

7.1.2.1. *Clinical improvement*

The WHO COVID-19 Clinical Improvement Ordinal Scale will be used to assess a clinical improvement score on Days 7, 14, and 28. See [Appendix 7](#) for details on the scale.

7.1.2.2. *Duration of hospitalization*

The number of days a patient has been hospitalized prior to study entry will be recorded in the eCRF.

Duration of hospitalization is the total number of days the patient is hospitalized during their participation in the study, up to Day 28.

7.1.2.3. *Virological clearance*

PCR testing for SARS-CoV-2 will be performed at a local or central laboratory at screening. Results of a confirmatory COVID-19 test already done as SoC can be used to determine eligibility. All subsequent tests (Day 1 and later) will be performed by a central laboratory. The PCR testing for SARS-CoV-2 will be collected during hospitalization as noted in the Schedule of Assessments ([Appendix 5](#)) and evaluated by the central laboratory.

Virological clearance will be measured by:

- **Time to viral clearance:** This endpoint will measure the time (days) to the first negative test for COVID-19.
- **Rate of change in viral load:** if quantitative PCR results are performed, the level of virus will be measured over time (days).

7.1.2.4. *Vital status*

Patient mortality will be recorded up to Day 28 and summarized in the analysis on Days 7, 14, and 28. Every effort will be made to ascertain vital status in all randomized patients (eg, with a vital records search) up to Day 28.

7.1.2.5. *Duration of ICU stay*

Duration of ICU stay is defined as the total number of days the patient is managed in the ICU during their participation in the study, up to Day 28. The date of the start and stop of the ICU stay must be recorded in the eCRF; no daily assessment is needed.

7.1.2.6. *Respiratory failure free*

The proportion of patients alive and respiratory failure free will be evaluated on Days 7 and 28. Respiratory failure is defined as the need for invasive mechanical ventilation, non-invasive ventilation, high-flow oxygen, or ECMO. The date of the start of the respiratory intervention must be recorded in the eCRF; no daily assessment is needed.

7.1.2.7. *COVID-19 symptoms*

COVID-19 symptoms assessment at the times indicated in the Schedule of Assessments in [Appendix 5](#) will evaluate: presence or absence of dry cough, dyspnea (shortness of breath/

difficulty in breathing), or chills/rigors, myalgia (muscle pain), headache, sore throat, and loss of taste or smell; other symptoms that could be related to COVID-19 will also be recorded.

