Patients will undergo assessment during hospitalization or could be discharged after start of study treatment any time after Day 2 if judged to be ready for discharge. If discharged, patients will then be requested to take study treatment at home (as prescribed) up to Day 14. End of Treatment (EOT) assessments will be performed at Day 14 (+2 days) (at home or site visit). A Day 5 (+/-1 day) visit (at home or site visit) will be performed if the patient is discharged prior to Day 5. If the patient is discharged after completion of treatment and before the follow up visit, he/she will be followed up on Day 28 (± 2 days) for study assessments (a telephone or telemedicine visit). Post discharge, assessments will be done by telephone or telemedicine, except for Day 5, Day 14, and Early Termination (ET) of Study Treatment. If the discharge, ET, or Early Withdrawal visit falls within the window of a scheduled Day visit, the assessments for the visits can be combined as one visit. The study design is summarized in [Figure 1](#).

Figure 1: Study Design

Abbreviations: BID = twice daily; DMC = Data Monitoring Committee; EOS = end of study; EOT = end of treatment; PK = pharmacokinetics; SoC = standard of care.

^a Sentinel cohort of 20 patients and an expansion cohort of 154 patients. The sentinel cohort will be treated with 100 mg antroquinonol or placebo BID. Enrollment will pause after the 20th patient in the sentinel cohort has started treatment. Once the 20th patient in the sentinel cohort has completed 14 days of treatment, an unblinded DMC will assess the data for safety, tolerability, efficacy, and PK in the sentinel cohort (interim analysis 1). The DMC will issue a recommendation to enroll patients for the expansion cohort, or to stop the study depending on the safety and futility assessment. Once the 80th patient has been enrolled, and completed 14 days of treatment, the DMC will review the safety, efficacy, and tolerability data (interim analysis 2). Enrollment may be restricted at the 100th patient until the DMC has completed the assessment to prevent excessive enrollment.

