3.4. Selection of doses in the study

Antroquinonol is already in clinical development, albeit in cancer patients, and shown to be well tolerated. Levels have included oral single doses of 50-600 mg and 200 mg BID (BID use has occurred due to a short plasma half-life of 1.30 to 4.33 hours). For the proposed clinical work, a starting dose of 100mg (given BID due to short half-life) is proposed based around anti-inflammatory activity in mouse efficacy work and the rat no-observed-adverse-effect-level (NOAEL) from toxicology testing. In the former, a 15-50 mg/kg/12.3 body surface factor was calculated to correspond to a 1.22-4.07 mg/kg human equivalent dose, or 85-285 mg for a 70 kg person. Therefore, a dose of 100 mg BID is within the animal efficacy range. The proposed dose is also supported by the rat study NOAEL on a mg/m² basis with an approximate 2-fold safety

margin [NOAEL in rat (30 mg/kg) x 6 (to convert dose in mg/kg to dose in mg/m²) = 180 mg/m² vs human 200 mg daily dose = 2.9 mg/kg x 37 (dose in mg/kg to dose in mg/m²) which converts to 108 mg/m² for a 70 kg person].

The safety of antroquinonol in patients with mild to moderate pneumonia caused by COVID-19 will be confirmed at 100 mg BID in the sentinel and expansion cohorts, which is within the animal efficacy range.

Treatment duration was selected based on the clinical presentation of the disease. Patients with COVID-19 experience systemic symptoms for approximately 7 to 10 days, and patients with disease progression but without ventilator use are typically hospitalized for 5 to 7 days. In a subset of patients, a cytokine storm can emerge resulting in complications. A treatment duration of 14 days should be adequate to treat the infection and prevent the immune response complications.

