- h Efficacy parameter assessments: [1] Confirmation of whether the patient is discharged to home, is in the hospital, or has worsened to require an ICU. The number of days a patient has been hospitalized prior to study entry will be recorded in the eCRF. [2] PCR testing for SARS-CoV-2 will be performed by a local or central laboratory at screening. Results of confirmatory COVID-19 test already done as standard of care can be used to determine eligibility. All subsequent tests will be performed by a central laboratory at baseline/Day 1, Day 5 (+/-1 day) and Day 14 (+2 days). Also at Follow-up/EOS if patient is hospitalized. Either nasopharyngeal or mid-turbinate samples are allowed for central testing. Only one method should be used throughout the study for the participant. [3] Clinical improvement score will be measured using the WHO COVID-19 Clinical Improvement Ordinal Scale (refer to [Appendix 7](#)). [4] Patient mortality will be recorded up to Day 28. Every effort will be made to ascertain vital status in all randomized patients (eg, with a vital records search) up to Day 28. [5] Respiratory failure is considered as patient need for invasive mechanical ventilation, non-invasive ventilation, high-flow oxygen, or ECMO. The date of the start of the respiratory intervention must be recorded in the eCRF; no daily assessment is needed. [6] COVID-19 symptoms (presence or absence of dry cough, dyspnea (shortness of breath/ difficulty in breathing), or chills/rigors, myalgia (muscle pain), headache, sore throat, and loss of taste or smell; other symptoms that could be related to COVID-19) will also be assessed during hospitalization, on discharge, ET/EOT and Follow-up/EOS visit (at the site, home visit, or via telephone or telemedicine if patient has been discharged).

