### 7.6.2.3 SARS-CoV-2 PCR Test

Time to virological clearance, measured as study days from start of treatment to first negative SARS-CoV-2 PCR test, will be evaluated using similar statistical methods as clinical improvement where in this case, the first negative SARS-CoV-2 PCR test is considered as an event. Patients will be censored on Day 28 if they have not yet shown SARS-CoV-2 PCR negative or have died by Day 28.

If quantitative SARS-CoV-2 PCR results are available, the following analyses will be conducted. Note that if a patient has tested negative, they are assumed to be negative until they are tested again and for negative test result, viral load is assumed to be half of the lower limit of detection.

- Rate of change in viral load will be estimated using a Mixed Model for Repeated Measurements model.

The model will include the treatment group, age at baseline ( $> 65$  years vs  $\leq 65$  years), remdesivir or other authorized treatments for COVID-19 use at baseline (yes vs no), log (viral load) at baseline, study day (numerical, 0 for baseline), and the interaction between study day and the treatment group as fixed factors, patient as random factor (random intercept and random slope).

The model will use natural-log-transformed viral load as the response variable.

An unstructured covariance structure will be used. In case of a convergence problem with the unstructured covariance matrix, the following structures with robust sandwich estimator for the standard error of the fixed effect estimates will be assessed in a sequential fashion: heterogeneous Toeplitz, heterogeneous first-order autoregressive, Toeplitz and compound symmetry.

The estimate of the study day\*treatment will be interpreted as the difference between treatment and placebo groups in terms of the rate of change in viral load. The estimate, standard error and p-value of study day\*treatment will be reported.

- Natural-log-transformed viral load with change from baseline will be summarized by treatment group and visit using descriptive statistics.
- Arithmetic mean (+SD) of natural-log-transformed viral load vs. time figure for each treatment group will be presented.

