## Statistical Analysis Plan

Sponsor Name: Golden Biotechnology Corporation  
Sponsor Protocol ID: GH Covid-2-001

Covance Study ID: 000000203201

- h Efficacy parameter assessments: [1] Confirmation of whether the patient is discharged to home, is in the hospital, or has worsened to require an ICU. The number of days a patient has been hospitalized prior to study entry will be recorded in the eCRF. [2] PCR testing for SARS-CoV-2 will be performed by a local or central laboratory at screening. Results of confirmatory COVID-19 test already done as standard of care can be used to determine eligibility. All subsequent tests will be performed by a central laboratory at baseline/Day 1, Day 5 and Day 14. Also at Follow-up/EOS if patient is hospitalized. Either nasopharyngeal or mid-turbinate samples are allowed for central testing. Only one method should be used throughout the study for the participant. [3] Clinical improvement score will be measured using the WHO COVID-19 Clinical Improvement Ordinal Scale (refer to Appendix 7 of the protocol). [4] Patient mortality will be recorded up to Day 28. Every effort will be made to ascertain vital status in all randomized patients (e.g., with a vital records search) up to Day 28. [5] Respiratory failure is considered as patient need for invasive mechanical ventilation, non-invasive ventilation, high-flow oxygen, or ECMO. The date of the start of the respiratory intervention must be recorded in the eCRF; no daily assessment is needed. [6] COVID-19 symptoms (presence or absence of dry cough, dyspnea (shortness of breath/ difficulty in breathing), or chills/rigors, myalgia (muscle pain), headache, sore throat, and loss of taste or smell; other symptoms that could be related to COVID-19) will also be assessed during hospitalization, on discharge, ET/EOT and Follow-up/EOS visit (at the site, home visit, or via telephone or telemedicine if patient has been discharged).

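### Protocol 7.1.2.3 can be read as limiting PCR swabs to inpatients, which Appendix 5 does not do for Days 5 and 14; where a site reads it so, the SAP's Day 28 censoring biases time to clearance against the arm discharged sooner

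*Protocol*

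**What the plan says.** Protocol 7.1.2.3, which describes how virological clearance is measured, states: "The PCR testing for SARS-CoV-2 will be collected during hospitalization as noted in the Schedule of Assessments".

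Protocol Appendix 5, footnote h, item 2 gives the sampling days: "All subsequent tests will be performed by a central laboratory at baseline/Day 1, Day 5 (+/-1 day) and Day 14 (+2 days". The inpatient condition appears only for the last visit: "Also at Follow-up/EOS if patient is hospitalized". SAP Appendix 2 repeats the rule, again with no inpatient condition on the two treatment-period swabs: "All subsequent tests will be performed by a central laboratory at baseline/Day 1, Day 5 and Day 14".

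On discharge, Protocol 3.1 says patients "could be discharged after start of study treatment any time after Day 2 if judged to be ready for discharge". Its visit plan is: "Post discharge, assessments will be done by telephone or telemedicine, except for Day 5, Day 14, and Early Termination (ET) of Study Treatment". The Appendix 5 table shows no PCR at the Discharge visit.

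SAP 7.6.2.3 sets the censoring rule for time to first negative PCR: "Patients will be censored on Day 28 if they have not yet shown SARS-CoV-2 PCR negative or have died by Day 28". The date of the last swab plays no part in it.

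**The concern.** The two texts give different rules for a patient who is at home on Day 5 or Day 14. Under the schedule the patient is swabbed. Under the literal words of 7.1.2.3 the patient is not.

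A missed swab would matter less if the patient left the risk set at the last test. The SAP instead carries the patient to Day 28 without an event, exactly like someone tested repeatedly and still positive. Whether clearance can be recorded then depends on still being in hospital. Duration of hospitalization is itself a secondary endpoint that the drug is meant to improve. A drug that shortens the stay would therefore lower its own recorded clearance rate. If sites differ in their reading, the analysis also mixes two versions of the endpoint.

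**Working it through.** The documents state no sample size, power or expected swab count for virological clearance, so there is no figure of the plan's own to reproduce. The check is a text comparison followed by calculations on stated assumptions.

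**Step 1: the texts side by side**

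| Swab | Protocol 7.1.2.3, literal | Appendix 5 and SAP Appendix 2, footnote h |
|---|---|---|
| Day 5 | inpatients | no inpatient condition |
| Day 14 | inpatients | no inpatient condition |
| Day 28 | inpatients | inpatients only |

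**Step 2: Day 14 swabs lost under the literal reading**

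Assume exponential stays with median m days and a share q not discharged by Day 14. The share lost is (1 − q) × (1 − 0.5^(14/m)). The documents give no discharge rate. I take m = 5 to 7 from Protocol 3.4. For q I use 0, 11% and 22%; the last two borrow the assumed Day 14 failure rates (100 − 89 and 100 − 78) as a rough proxy.

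| q | m = 5 | m = 7 | m = 10 |
|---|---|---|---|
| 0 | 86% | 75% | 62% |
| 11% | 76% | 67% | 55% |
| 22% | 67% | 58% | 48% |

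**Step 3: effect on the hazard ratio**

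Assumptions:
- median stay 5 days on antroquinonol and 7 on placebo
- discharge only after Day 2, then exponential
- 15% never discharged in either arm
- exponential clearance, independent of discharge
- swabs on Days 5 and 14, and on Day 28 if still in hospital

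Hand check with median clearance of 10 days in both arms. The share in hospital on day d is 0.15 + 0.85 × 0.5^((d − 2)/(m − 2)). For Days 5, 14 and 28 this gives 0.575, 0.203 and 0.152 (m = 5), and 0.711, 0.311 and 0.173 (m = 7). Cumulative clearance is 0.293, 0.621 and 0.856, so the increments are 0.293, 0.328 and 0.235.

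- Recorded clearance, antroquinonol: 0.575 × 0.293 + 0.203 × 0.328 + 0.152 × 0.235 = 0.27
- Recorded clearance, placebo: 0.711 × 0.293 + 0.311 × 0.328 + 0.173 × 0.235 = 0.35

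True clearance is identical, yet placebo records more of it. With swabs per schedule, both arms record about 0.66. Simulated Cox hazard ratios (below 1 means slower clearance on antroquinonol):

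| Median clearance (days) | Swabs per schedule, Day 28 censoring | Inpatients only, Day 28 censoring | Inpatients only, censored at last PCR |
|---|---|---|---|
| 7 in both arms | 0.99 | 0.75 | 0.99 |
| 10 in both arms | 1.00 | 0.76 | 1.00 |
| 14 in both arms | 0.97 | 0.76 | 0.99 |
| 7 antroquinonol, 10 placebo | 1.28 | 0.91 | 1.30 |

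The bias needs both ingredients. It is essentially absent when swabs follow the schedule, and essentially absent when inpatient-only swabs are censored at the last PCR.

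**Step 4: how far the size depends on the model**

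I kept the 5 versus 7 day stays and varied the rest: stay distribution exponential or Weibull with shape 1.5; 0 to 22% undischarged; with or without a Day 28 inpatient swab. With no true difference, the hazard ratio is about 0.6 to 0.8. The low end arises when nearly everyone is discharged by Day 14.

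For a true benefit, take clearance of 25% by Day 5 and 60% by Day 14 on placebo, against 35% and 75% on antroquinonol. The hazard ratio is about 1.5 with full swabbing. Under inpatient-only swabbing it falls to between about 0.75 and 1.12, depending on the settings. Attenuation is consistent; reversal is not.

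**The case against.** The best counter-argument is that the documents mostly resolve the conflict themselves. The sentence in 7.1.2.3 points to the schedule, and Protocol section 7 calls adherence to the schedule essential. Footnote h limits only the Day 28 swab, and that limit would be redundant if all swabs were inpatient-only. The endpoint names Days 5 and 14, and discharged patients have in-person visits on just those days. This stands: swabbing everyone is the more natural reading. It does not remove the words about hospitalization from the section that describes the endpoint. Nor does footnote h tell sites to swab discharged patients, whereas its symptom item and the laboratory item in footnote i do mention them.

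A second objection is that the sizes rest on assumptions. This also stands. Protocol 3.4 says "patients with disease progression but without ventilator use are typically hospitalized for 5 to 7 days", which describes a subgroup and serves to justify treatment duration. It is not a discharge forecast for this trial and does not count the stay from randomization. Inclusion criterion 3 (oxygen saturation below 94%) may also select patients who stay longer.

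A reader might infer that the trial will lose most of its Day 14 swabs, or that a real antiviral benefit would be reversed. The documents support neither. The first needs every site to choose the less natural reading, together with short stays. The second depends on the assumed clearance rates and on how many patients remain in hospital.

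Finally, the bias comes from the Day 28 censoring rule as much as from 7.1.2.3. That is correct, and it is why the fix has two parts.

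**Conclusion.** The inconsistency is real and lies in the current text. Its effect is conditional: it arises only at sites that apply 7.1.2.3 literally, and it becomes a bias only because the SAP keeps unswabbed patients at risk to Day 28.

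The direction held in every model tried: the arm discharged sooner looks worse on clearance. If every site used the inpatient-only reading, stays were 5 versus 7 days and true clearance were equal, the hazard ratio would be about 0.6 to 0.8 instead of 1. Mixed practice falls between that and no bias. Equal stays in the two arms would cost information but would not favour either arm.

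The figures assume that clearance and discharge are independent and that the drug shortens the stay by two days; neither comes from the documents. The primary endpoint and sample size are untouched. The viral-load model would lose the same swabs, but I have not quantified that.

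**What to change.** 1. Amend Protocol 7.1.2.3 to match Appendix 5: Day 5 (±1) and Day 14 (+2) samples are collected from all patients, including discharged patients at the planned home or site visit; the Day 28 sample is collected only if the patient is hospitalized.
2. In SAP 7.6.2.3, censor living patients without a negative result at their last PCR. Deaths stay as not cleared to Day 28.
3. In the same section, report the number swabbed on Day 5 and on Day 14 by arm and by discharge status, so that uneven sampling is visible whatever sites have already done.

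The cost is a short protocol clarification, a changed censoring rule and one descriptive table. No visit is added. The new rule has its own assumption, that discharge is non-informative for clearance given the model. If patients who clear early also go home early, some bias would remain wherever swabs were missed, so item 1 is the main protection and item 2 the safeguard.
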